2.4 Randomisation

Randomisation will take place when all the screening procedures and the biopsy visit are completed, and the patient is eligible for enrolment in the study. The randomisation in the study will be applied using simple randomisation, with equal allocation ratio (1:1). All patients with sufficient RNA for analysis will be randomised using simple randomisation (1:1 allocation ratio) into the Control or the Treatment arm according to biomarker arm.

Patients allocated to the control arm of the study, will be subsequently randomised again using simple randomisation with equal treatment allocation ratio (1:1) to Abatacept and Methotrexate therapy or placebo and Methotrexate therapy.

Once the biopsy sample has been received by the central laboratory, patients will be stratified into 2 groups, CD80/CD86 positive (biomarker+) or CD80/CD86 negative (biomarker-) and randomised 1:1 to receive either Abatacept and Methotrexate therapy or placebo and Methotrexate therapy.

3. General Analysis Definitions

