2.3 Sample size determination

The primary aim of the study is to demonstrate that patients in the "Drug target biomarker" group (Group 1) will have a higher response rate than the "No drug target biomarker" groups (Group 2 and 3)- see section 2.2 for trial diagram.

Using change in CDAI score from baseline (delta CDAI) as the primary outcome, a difference in delta CDAI between the two comparison groups of 10, with a Standard Deviation of 14.34. These are the values that were observed when analysing the difference in delta CDAI between biomarker positive and biomarker negative patients treated with MTX in the PEAC study. Although PEAC patients were not treated with Abatacept, this comparison is expected to be even more in favour of the biomarker positive group using Abatacept together with MTX. Thus, basing the power calculation on the PEAC observed difference is a conservative assumption.

With these assumptions, 90 patients would be needed to detect a significant difference of 10 in delta CDAI with 90% power. Since this would only be for Group 1 and Group 3 (45 patients each), a total of 180 patients would be sufficient for 90% power in the whole trial (Figure 1 Section 2.6). If we assume a 5% dropout rate and also account for an expected 5% of patients that have insufficient RNA for the Nano-string analysis (based on results from the STRAP trial), 200 patients in the whole trial would be sufficient to detect a significant difference (Group 1 vs Group 3) of 10 in delta CDAI with 90% power.

All power calculations were performed using the "twomeans" package in STATA, version SE 18.

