4.7 General considerations

For each treatment group and biomarker, the following will be presented:

- Number and percentage of subjects screened, not randomised/assigned treatment, randomised/assigned treatment, randomised/assigned treatment and not started treatment, discontinued, and completed.
- Number and percentage of subjects randomised at each site.
- Number and percentage of subjects in each analysis set (ITT) overall and by visit.
- Number and percentage of subjects excluded from each analysis set by reason for exclusion.
- Number and percentage of withdrawals (withdraw consent to any further participation in the trial) and treatment cessation, by reason for discontinuation and visit.

5. Interim analysis and timing for analysis

No interim analysis is planned for the current trial. However, the TSC will review the accruing trial data every year during the recruitment phase of the study and assess whether there are any safety issues that should be brought to participants' attention or any reasons for the trial not to continue. TSC reports will consist of an open report where the accrual data will be described without any information on the arm patients have been allocated to, and a closed report where any safety issues by treatment arm will be presented. No stopping rule will be used. See section 9 for further detail. The trial data will be analysed following database lock.

6. Efficacy analysis

The listed measures in Table 2 are to be used in the analyses. The analyses will be carried out in STATA 18 or higher.

In hypothesis testing, the null hypothesis is rejected at (two-sided) significance level 0.05 unless otherwise specified.

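### Simple randomisation after sorting by CD80/CD86 status leaves the abatacept/placebo split within each biomarker group to chance; blocks within biomarker status would protect against unlucky splits, for a small gain in average power

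*SAP*

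**What the plan says.** SAP section 2.4 sets one method for the whole study: "The randomisation in the study will be applied using simple randomisation, with equal allocation ratio (1:1". It repeats that method for the arm step ("All patients with sufficient RNA for analysis will be randomised using simple randomisation (1:1 allocation ratio) into the Control or the Treatment arm") and for the drug step in the control arm, where patients "will be subsequently randomised again using simple randomisation with equal treatment allocation ratio (1:1".

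Its last paragraph says that, once the central laboratory has the biopsy, "patients will be stratified into 2 groups, CD80/CD86 positive (biomarker+) or CD80/CD86 negative (biomarker-) and randomised 1:1" to abatacept or placebo, each with methotrexate. That sentence names no method of its own, so the study-wide statement governs it. No block, minimisation or other restricted scheme appears anywhere in the SAP.

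Section 2.3 sizes the trial on 45 patients in each of Groups 1 and 3. Section 2.1 defines that contrast as biomarker positive versus biomarker negative among abatacept patients. Section 6.1.1 also describes an abatacept-placebo difference within each biomarker group.

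**The concern.** Independent 1:1 draws made separately within two strata have the same distribution as independent 1:1 draws made without strata. Stratifying an allocation controls the split only if allocation is also restricted within the stratum, for example by blocks. Section 2.4 names the strata but no restriction.

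Only abatacept patients enter Group 1 versus Group 3, so the size of that comparison depends on how many patients in each biomarker group happen to draw abatacept. The abatacept-placebo difference within biomarker groups depends on the same split. Neither comparison is biased by this. What is at stake is precision, and how far the realised power may fall below the planned 90%.

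**Working it through.** **Inputs from the SAP.** Section 2.3 gives "a difference in delta CDAI between the two comparison groups of 10, with a Standard Deviation of 14.34" and states that "90 patients would be needed to detect a significant difference of 10 in delta CDAI with 90% power", taken as 45 per group, 180 in the whole trial, and 200 after 5% dropout and 5% insufficient RNA. Section 6 gives the level: "the null hypothesis is rejected at (two-sided) significance level 0.05 unless otherwise specified".

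**Assumptions, not in the SAP.** 180 patients analysed; 1:1 abatacept/placebo in both biomarker groups; biomarker prevalence of 50% (which 45 in each of Groups 1 and 3 implies), with 40% and 30% to show the range.

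**1. Reproduce the plan's figure.**
- Normal approximation: n per group = 2 × (1.960 + 1.282)² × 14.34² / 10² = 43.2, so 44.
- Two-sample t-test: degrees of freedom n1 + n3 − 2, noncentrality 10 / (14.34 × √(1/n1 + 1/n3)). At 45 and 45 the noncentrality is 10 / (14.34 × 0.2108) = 3.31 and power is 90.5%; at 44 and 44 it is 89.9%. So 45 per group is right.
- 180 / 0.90 = 200. The sample size reproduces.

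**2. Drug split under simple randomisation.** With 90 patients in a biomarker group, the number on abatacept is Binomial(90, 0.5): mean 45, SD √(90 × 0.25) = 4.7, 95% range 36 to 54.
- The chance of a split of 40:50 or worse in a given biomarker group is 34%.
- The chance that Group 1 or Group 3 has fewer than 45 is 71%.
- Power is 86.9% at 40 versus 40 and 83.1% at 36 versus 36.
- Within a biomarker group, a 36:54 split inflates the variance of the drug effect by (1/36 + 1/54) / (2/45) = 1.042, about 4%.

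**3. Drug split under blocks.** With blocks of 4 (an assumed size) the number on abatacept stays within 44 to 46 of 90.

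**4. Power over the whole process.** The number of positives is drawn as Binomial(180, prevalence). The abatacept number is then drawn as Binomial(group size, 0.5) for simple randomisation, or set to half of each group for blocks. Power is calculated at each realised pair of group sizes.

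| Biomarker positive | Mean power, simple | Mean power, blocks | 5th percentile, simple | 5th percentile, blocks |
|---|---|---|---|---|
| 50% | 90.0% | 90.4% | 85.8% | 89.8% |
| 40% | 88.7% | 89.1% | 83.7% | 87.3% |
| 30% | 84.1% | 84.7% | 75.8% | 80.3% |

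Blocks raise mean power by 0.4 to 0.6 points and the 5th percentile by about 4 points (3.6 to 4.5). Moving from 50% to 30% positive costs 5.7 points of mean power even with blocks (90.4% to 84.7%).

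**The case against.** **Simple randomisation is valid at this size, and the average gain is under one point of power.** This stands. The planned sample size is not wrong, and the point is a refinement of the design.

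**Stratified may only mean classified.** Elsewhere the SAP uses the word for sorting patients by biopsy (sections 2 and 3.1.2), and sorting does define the analysis groups. A reader might infer that section 2.4 promises balance and contradicts itself, or that its stratification does nothing at all. The text does not support that; it is ambiguous. On either meaning, though, the drug split is uncontrolled.

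**The allocation sequence is not settled.** Section 2 describes an arm randomisation first and then, in the intervention arm, states a 1:1 draw only for patients without the target biomarker. Section 2.4 also has an arm step, but then describes a 1:1 drug draw within both biomarker groups. The calculation follows the latter and would change under the former. This stands, and it has to be resolved before anyone can say where blocks apply.

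**Blocking the drug step cannot balance prognosis in Group 1 versus Group 3.** Correct: that contrast compares biomarker groups, which are not randomised. Blocks control its size and the drug comparison within each biomarker group, nothing more.

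**Blocks make allocation a little more predictable.** True, but section 1 keeps investigators and site staff blind to the intervention and the arm, which limits the risk.

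**Conclusion.** The point holds as a minor design weakness. Section 2.4 leaves the abatacept number in each biomarker group to chance, while section 2.3 assumes 45. Blocks would raise mean power by about half a point and the 5th percentile by about 4 points at every prevalence tried. This rests on 180 analysed, 1:1 drug allocation in both biomarker groups, and the SAP's difference and SD.

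Two stronger readings should be avoided:
- A reader might infer that blocks sharply raise the chance of reaching 90% power. That is so only at 50% prevalence, because 45 versus 45 gives 90.5%, just above the threshold. At 40% positive the chance is 36% with simple randomisation and 22% with blocks; at 30% it is 6% and 0%. Blocks narrow the spread; away from 50% they do not restore 90%.
- A reader might quote a 16:29 split with 9% variance inflation. That belongs to a group of 45; the biomarker groups assumed here hold about 90, where the extreme is 36:54 and 4%.

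Biomarker prevalence, which the SAP does not give and blocking cannot change, matters more for power than the drug split.

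**What to change.** 1. Reconcile sections 2 and 2.4 on the sequence: arm first and then drug, or drug within biomarker group. State which step applies to which patients.
2. Say whether stratified in section 2.4 means classified for analysis or stratified randomisation.
3. For patients still to be randomised, replace simple randomisation at the abatacept/placebo step with permuted blocks of randomly varying, undisclosed size within CD80/CD86 status. If the biomarker result is not available at the control-arm drug step, block within the control arm instead.

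The cost is a new allocation list, an amendment to the randomisation wording, and slightly more predictable allocation. The sample size, endpoint and visits do not change. The SAP does not show how far recruitment has gone. If no patients remain to be randomised, only the first two items apply, so that reports do not claim a balance that the method did not provide.

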3.1 Study timelines and visit definitions

3.1.1 Study timelines

Data cleaning will be carried out periodically throughout the trial duration and final cleaning will take place up to 4 months after Last Patient Last Visit (LPLV). The main analyses will be carried out following database lock, in time for the clinical study report which will be submitted to the REC. The trial results will be uploaded to the EudraCT website.

3.1.2 Visits

Patients who consent are screened and undergo a synovial biopsy. Randomisation will take place when all the screening procedures are completed, and the biopsy is performed, and the patient is eligible for enrolment in the study (Protocol section 6).

A synovial biopsy will be carried out for each patient before the baseline visit (Protocol section 2.6). This initial synovial biopsy is mandatory as part of the patient stratification process; however, the subsequent week 16 synovial biopsy will remain optional.

Patients receive Abatacept + MTX or Placebo + MTX at Baseline (week 0) visit 3 depending upon randomisation outcome. All baseline assessments are performed prior to commencement of therapy.

After baseline, all patients will be monitored on a 4 weekly basis (\pm 7 days).

3.2 Study populations

3.2.1 ITT population

ITT population includes all the patients who were enrolled in the trial and were randomised/assigned treatment according to biomarker. All patients will be analysed according to the randomisation/treatment allocation including any withdrawals after randomisation/treatment allocation.

There are two types of withdrawal defined; full withdrawal from the study (the patient does not attend any further visits) or withdrawal from trial treatment (treatment cessation). The data collection and follow up requirements are specified in Sections 15 of the trial protocol.

ITT analysis will be used for all analyses except for the safety analysis in Section 14.9.

3.2.2 Other populations

Definition/Description of Other population is in the Protocol Section 14.6

3.2.3 Safety analysis set (SAF)

Safety analysis set consists of patients who received at least one dose of the trial medication. This population is identical to the ITT population except that patients will be analysed according to their actual treatment in case this differs from the scheduled treatment. This population set will be used to report the safety data.

3.3 Study Endpoints

3.3.1 Primary endpoint

The primary endpoint is the change in CDAI between baseline and at 16 weeks. This endpoint is a continuous outcome.

A responder is defined as a patient who achieved an improvement of 10 units in CDAI: 10 unit reduction is regarded and an improvement.

3.3.2 Secondary endpoints

- 1) Percentage of patients with DAS28<3.2 (LDA) at 16 weeks.
- 2) Percentage of patients deemed responders using American College of Rheumatology 50 (ACR50) measure at 16 weeks.
- 3) Percentage of patients with CDAI remission at 16 weeks.
- 4) Change in HAQ-DI at 16 weeks from baseline.
- 5) Change in SF-36 at 16 weeks from baseline

3.3.3 Exploratory endpoints

- 1) Percentage of patients deemed responders using American College of Rheumatology 20/70 (ACR20/70) measure at 16 weeks.
- 2) Percentage of patients with ACR/EULAR Boolean remission at 16 weeks.
- 3) Mean % change in CDAI score and DAS28 at 16 weeks.

- 4) Change in FACIT, ESS, and EQ-5D score at 16 weeks from baseline
- 5) The association between synovial histology and ultrasound measures of inflammation, drug response rates, disease outcome and disability.
- 6) SAEs from 0 to 16 weeks for all patients
- 7) Change in 12-max summary measure of US 2D synovial thickness (ST) grey scale and power Doppler (PD) signal from baseline at 16 weeks.
- 8) Changes from baseline to week 16 in the total histopathological synovitis score.

4. Descriptive statistics

All the following descriptive statistics of patients in the study (will be presented separately and then combined.

Demographics and patient characteristics are listed in the table below. For further information, please see Protocol Section 7.5

Table 1: List of demographics and characteristics.

Variable type	Variables
Demographics	Age, Gender, Ethnicity, Medical History
Diagnostics	2010 ACR/EULAR RA classification criteria (joint involvement, serology, acute phase reactant, symptom duration), rheumatoid factor, CCP, disease duration
Disease activities	ACR/EULAR core set, DAS28, CDAI, VAS
Physical function	HAQ,
Fatigue score	FACIT
Health status	SF-36, EQ-5D-5L
Sleepiness	ESS
Vital signs	Weight, Height, BMI, blood pressure (systolic, diastolic), pulse, temperature
Cardiovascular risk factors	Alcohol status, smoking status and smoking years, lipid lowering agent, ischemic heart disease, diabetes, hypertension, family history
Routine blood tests	ESR, CRP, Hb, Haematocrit, WBC, Platelets, Neutrophils, Lymphocytes, ALT, AST, Creatinine, Urea, Sodium, Potassium, eGFR, Red blood cell count, Mean cell haemoglobin, Mean cell volume
Image assessments	Radiograph scores (Sharp van der Hyde scores, including erosion scores, joint space narrowing and total) Ultrasound scores (Power doppler and Synovial thickening)

4.1 Demographics and baseline characteristics

The summary of continuous variables will include the number of subjects, the mean and standard deviation, the median, the minimum and the maximum as well as the numbers with missing values. For categorical variables, the frequencies and percentages will be presented, where the percentages will be based on the complete cases (without missing data). A summary will be presented overall, by biomarker (positive/negative) and by treatment. At baseline, the summary is applied on each of the variables listed in Table 1.

4.2 Characteristics collected at 16 weeks

The same summary as for the baseline will be carried out at 16 weeks, by biomarker and by treatment.

4.3 Prior and concomitant therapies

Prior and concomitant therapies are defined in the Protocol Section 11.15.

4.4 Baseline biomarker

Baseline biomarker will be summarised using frequency and percentage and displayed by treatment.

4.5 Study drug

For each study drug exposure, number and percentage of patients will be reported by visit and dose received.

Adherence to the planned dose regimen of study medication will be summarised (dose modification, reduction, delay) by visit and treatment.

4.6 Protocol violations

All major protocol violations will be summarised by type of violation, treatments groups and pathotype.

4.7 General considerations

For each treatment group and biomarker, the following will be presented:

- Number and percentage of subjects screened, not randomised/assigned treatment, randomised/assigned treatment, randomised/assigned treatment and not started treatment, discontinued, and completed.
- Number and percentage of subjects randomised at each site.
- Number and percentage of subjects in each analysis set (ITT) overall and by visit.
- Number and percentage of subjects excluded from each analysis set by reason for exclusion.
- Number and percentage of withdrawals (withdraw consent to any further participation in the trial) and treatment cessation, by reason for discontinuation and visit.

5. Interim analysis and timing for analysis

No interim analysis is planned for the current trial. However, the TSC will review the accruing trial data every year during the recruitment phase of the study and assess whether there are any safety issues that should be brought to participants' attention or any reasons for the trial not to continue. TSC reports will consist of an open report where the accrual data will be described without any information on the arm patients have been allocated to, and a closed report where any safety issues by treatment arm will be presented. No stopping rule will be used. See section 9 for further detail. The trial data will be analysed following database lock.

6. Efficacy analysis

The listed measures in Table 2 are to be used in the analyses. The analyses will be carried out in STATA 18 or higher.

In hypothesis testing, the null hypothesis is rejected at (two-sided) significance level 0.05 unless otherwise specified.

6.1 Main analyses

6.1.1 Primary endpoint

The primary endpoint of the study will be a continuous outcome of CDAI measure at 16 weeks (visit 7).

The primary analysis will assess the difference in the CDAI comparing the difference in response between the abatacept and placebo groups with the biomarker positive group against the difference in response between the abatacept and placebo groups with the biomarker negative group. This analysis will be on an ITT basis according to original randomisation allocation.

The differences between the groups on the primary outcome will be tested with a mixed-effects model with time as a continuous variable. The CDAI is measured at five time points: (1) Baseline, (2) 4 Weeks, (3) 8 Weeks, (4) 12 Weeks, (5) 16 Weeks. The baseline measurement for the primary outcome is the CDAI score after randomisation. This measurement will be included in the analysis as a covariate.

The mixed-effects model results will be presented as P values and 95% CI. In the mixed-effects model we will use both an 'unstructured' and a '1. order autoregressive' covariance matrix and choose the matrix resulting in the lowest Bayesian information criterion. To assess, if the underlying assumptions behind the mixed-effects model analysis are fulfilled, we will investigate normal quantile plots of residuals, standardized residuals, and random effects. If the underlying assumptions behind the mixed-effects model analysis are clearly violated then we will use a generalized estimation equation for the analysis.

The planned primary analysis is a mixed-effects model adjusted for centre and patient comparing the outcome of CDAI between treatment groups in the biomarker arm (Group 1) and non-biomarker arms (Group 3).

A p-value of less than 0.05 will be taken to indicate statistical significance.

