2.1 Study objectives

Primary objective: The primary objective of this trial is to determine whether synovial molecular profiles (=drug target signatures) can inform treatment response to abatacept in early RA..

To this aim, we will compare the change in Clinical Disease Activity Index (CDAI) score at 16 weeks between the biomarker positive and the biomarker negative patients within the abatacept group (i.e. Group 1 vs Group 3) Fig.1 Study Scheme diagram. The primary trial hypothesis is that biomarker positive patients treated according to their highest expressed biomarker will have lower CDAI response at 16 weeks compared to biomarker negative patients.

[figure not shown]
This primary analysis has been chosen as we want to establish a difference in response rates in the treatment in the biomarker arm first, and the trial has been powered for this.

Secondary objectives:

The following analysis will be done:

- Compare patients treated according to their biomarker in the intervention arm against the control arm as a whole (i.e. Group 1 vs 3+4), to determine the enrichment in response in the treatment allocation arm vs the standard of care response rate.
- II. Assess the efficacy of treatment allocation according to biomarker compared to random allocation, we will compare the biomarker positive patients in the intervention arm vs the biomarker positive patients in the control arm (i.e. Group 1 vs Group 4)
- III. Assess the efficacy of the strategy as a whole against the current clinical practice by comparing the control vs intervention arm (i.e. Groups 1 + 2 vs Group 3+4)

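### SAP section 6.1.1 states two incompatible primary analyses, and the stated 90% power applies only to Group 1 vs Group 3

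*SAP*

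**What the plan says.** Four places in the SAP bear on the primary contrast.

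- Section 2.1 compares CDAI change "between the biomarker positive and the biomarker negative patients within the abatacept group (i.e. Group 1 vs Group 3". It adds that this analysis was chosen as primary and that the trial is powered for it.
- Section 2.3 opens by setting Group 1 against Groups 2 and 3 together. The calculation that follows is for Group 1 vs Group 3 only and concludes that "200 patients in the whole trial would be sufficient to detect a significant difference (Group 1 vs Group 3) of 10 in delta CDAI"; the power given for this is 90%.
- Section 6.1.1, second paragraph, describes the primary analysis as "comparing the difference in response between the abatacept and placebo groups with the biomarker positive group against the difference in response"; the second difference is the one seen in the biomarker-negative group.
- Section 6.1.1, near its end, describes the planned primary analysis as a mixed-effects model "comparing the outcome of CDAI between treatment groups in the biomarker arm (Group 1) and non-biomarker arms (Group 3".

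Section 6.1.2 then lists 1 vs 3 and 1+2 vs 3+4 as comparisons guided by those of the primary analysis. No section gives an effect size or power for an interaction.

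**The concern.** Both descriptions in 6.1.1 are current text, both are called primary, and neither is marked as supportive. They answer different questions. The first asks whether the effect of abatacept over placebo depends on biomarker status, and it needs placebo patients. The second asks whether biomarker-positive patients do better than biomarker-negative patients when both receive abatacept, and it uses no placebo patients.

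The answers can differ. Section 2.3 takes its planning difference of 10 from biomarker-positive and biomarker-negative patients treated with methotrexate, without abatacept. If a similar difference appears under placebo plus methotrexate in this trial, Group 1 vs Group 3 could be significant while the interaction is close to zero. The published conclusion would then depend on which sentence of 6.1.1 was followed, and the 90% power statement would cover only one of them.

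**Working it through.** **Inputs from the SAP.** Section 6: "the null hypothesis is rejected at (two-sided) significance level 0.05 unless otherwise specified". Section 2.3: "a difference in delta CDAI between the two comparison groups of 10, with a Standard Deviation of 14.34"; "90 patients would be needed to detect a significant difference of 10 in delta CDAI with 90% power"; and "this would only be for Group 1 and Group 3 (45 patients each), a total of 180 patients would be sufficient" for the whole trial.

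**Assumptions not in the SAP.** Four equal biomarker-by-drug cells of 45, inferred from 180 = 4 × 45. The same SD in every cell. The interaction size is unknown, so a range is shown.

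**1. Reproduce the plan's figure (Group 1 vs Group 3).**
- Normal approximation: n per group = 2 × [14.34 × (1.960 + 1.282) / 10]² = 43.2, rounded up to 44.
- Noncentral t: 44 per group gives 89.9% and 45 gives 90.5%, so 45 per group, or 90 patients, are needed.
- Standard error at 45 per group: 14.34 × √(2/45) = 3.02.
- Total: 4 × 45 = 180. With 10% losses, 180 / 0.90 = 200.

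The 90%, 90, 180 and 200 all reproduce for this contrast.

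**2. Apply the same inputs to the interaction.**
- Standard error = 14.34 × √(4/45) = 4.28. This is √2 times the two-group value, so the variance is doubled.
- Power by noncentral t with 180 − 4 = 176 degrees of freedom:

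| Interaction (CDAI points) | Power |
|---|---|
| 5 | 21% |
| 7.5 | 41% |
| 10 | 64% |
| 12 | 80% |
| 15 | 94% |

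- Interaction detectable with 90% power: (1.960 + 1.282) × 4.275 = 13.9 points.
- With a 1:2 biomarker split (cells of 30, 30, 60 and 60), the standard error is 14.34 × √(2/30 + 2/60) = 4.53, and power for an interaction of 10 falls to 59%.

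**3. How the two contrasts relate.** Measured as CDAI reduction, the interaction equals the biomarker difference under abatacept minus the biomarker difference under placebo.
- If the methotrexate-based difference of 10 also holds under placebo plus methotrexate, and Group 1 vs Group 3 is exactly 10, the interaction is 10 − 10 = 0.
- An interaction of 10 would then need a Group 1 vs Group 3 difference of 20.

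**4. Group labels.** Section 2.1 treats Group 3 as biomarker-negative patients on abatacept. It also treats Groups 3 and 4 together as the whole control arm, with Group 4 as the biomarker-positive controls. Section 2.3 treats Groups 2 and 3 as the groups without the biomarker. Section 2.4 randomises the control arm 1:1 to abatacept or placebo. On that description the control arm also contains biomarker-negative placebo patients, who have no place in Group 3 or Group 4 as section 2.1 describes them. The scheme diagram is not visible in the text reviewed, so the intended map could not be checked.

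**The case against.** The SAP leans clearly one way. Section 2.1 names Group 1 vs Group 3, section 2.3 powers it, 6.1.1 calls it the planned primary analysis and 6.1.2 lists 1 vs 3 again. Section 1 requires written agreement from the Lead and Independent Statisticians for SAP changes and justification of any deviation. On this view the interaction sentence is a stray sentence, not a rival primary analysis. That argument limits the risk of selection after unblinding, but the contradiction remains: the sentence says what the primary analysis will assess.

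A reader might infer that the trial has only 64% power. The documents do not support that. The 10 in section 2.3 is a two-group difference, and no interaction size is given anywhere. The 64% depends on carrying the 10 over and on four cells of 45. It could be generous, given step 3 of the working, or pessimistic if abatacept acts strongly only in biomarker-positive patients.

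Two further cautions stand. The calculations use the SD of raw change, whereas 6.1.1 plans a baseline-adjusted repeated-measures model. If that model lowers the residual SD, both powers rise, but with equal cells the interaction keeps its doubled variance. And the second 6.1.1 sentence is itself loosely worded: read alone, it could mean comparing treatments inside each biomarker group. That is a further reason to rewrite it.

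**Conclusion.** The contradiction is real and concerns the primary test, so it must be resolved before unblinding. Section 6.1.1 gives two primary analyses with different null hypotheses, and the opening of 2.3 adds a third comparison. The stated 90% power is correct for Group 1 vs Group 3 with 45 each and does not apply to the interaction. What power the interaction would have is conditional: it rests on an SD of 14.34, four equal cells of 45 and an interaction size that the SAP does not state, and it falls if biomarker prevalence is unequal. The documents do not support saying that the trial as designed is underpowered, or that the two analyses have equal standing in the SAP.

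**What to change.** Before unblinding:

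1. Define Groups 1 to 4 once, each by biomarker status, randomised arm and drug, and use those definitions throughout. Without this, identical wording that relies on the labels would still be ambiguous.
2. State one primary contrast in identical words in 2.1, 2.3 and 6.1.1.
3. If it is Group 1 vs Group 3, as most of the SAP indicates: remove the difference-of-differences sentence from the primary definition, report the interaction as a secondary analysis, and delete the reference to Groups 2 and 3 from the opening of 2.3. The rank of the interaction among the secondary analyses is the sponsor's choice.
4. If it is the interaction: change 2.1 and 2.3 to match, and replace the 90% claim with the power at the planned sample size for a stated and justified interaction.

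The first route costs SAP wording only. The second needs no extra patients if the restated power is accepted. Keeping 90% power for an interaction of 10 would take 4 × [14.34 × (1.960 + 1.282) / 10]² = 86.4, or 87 per cell. That is 348 evaluable patients and about 348 / 0.90 = 387 recruited.
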